16. SAFETY OUTCOMES

All outputs for safety outcomes will be based on the SAF.

There will be no statistical comparisons between the treatment groups for safety data, unless otherwise specified with the relevant section.

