Duration of Treatment:	The approximate planned duration of participation for each patient will be up to 61 days: 7 to 14-day screening period, up to 9 days treatment (three treatment periods of 3 days each separated by 7 to 14 days) and an end of study visit 4 to 10 days after the last treatment visit (Day 4 of Treatment Period 3).
Statistical Methods:	Treatments will be compared using analysis of covariance adjusting for treatment, period, patient and baseline. Multiplicative models will be used for FEV ₁ and outcome from whole body plethysmography and additive models for blood pressure, pulse rate and ECG heart rate. RPL554 doses will first be compared to placebo using a closed test procedure starting with the highest dose of RPL554.
Sample Size:	This is a complete block three-way crossover study. Assuming a residual coefficient of variation of 6% for peak FEV ₁ , 70 patients will give an 80% power to detect a pairwise difference in FEV ₁ of 50 mL.

Verona Pharma plc CONFIDENTIAL Page 8 of 66

TABLE OF CONTENTS AND LIST OF TABLES AND FIGURES

Table of Contents

SPC	NSOI	R SIGNA	ATURE PAGE	2
INV	ESTI	GATOR	SIGNATURE PAGE	3
COl	NFIDE	ENTIAL	ITY STATEMENT	3
COl	NTAC	T LIST .		4
DET	TAIL (OF AME	ENDMENTS SINCE THE PREVIOUS VERSION	5
SYN	IOPSI	S		6
TAE	BLE O	F CONT	TENTS AND LIST OF TABLES AND FIGURES	9
	Tabl	e of Cor	ntents	9
	List	of Table	es and Figures	12
LIS	ΓOF	ABBRE	VIATIONS AND DEFINITION OF TERMS	13
1	INT	RODUC	TION	14
	1.1	Diseas	e and Study Medication Review	14
	1.2	Summ	ary of Risks and Benefits	16
2	OBJ	ECTIVE	ES	17
	2.1	Primar	y Objective	17
	2.2	Second	dary Objectives	17
	2.3	Explor	ratory Objectives	17
3	INV	ESTIGA	ATIONAL PLAN	18
	3.1	Overal	1 Study Design and Plan Description	18
	3.2	Discus	sion of Study Design, including the Choice of Control Groups	19
	3.3	Planne	d Duration of the Study	19
	3.4	Definit	tion of the End of the Study	19
4	SEL	ECTION	N OF STUDY POPULATION	20
	4.1	Inclusi	on Criteria	20
	4.2	Exclus	ion Criteria	21
	4.3	Remov	val of Patients from Therapy or Assessment	22
		4.3.1	Study Treatment Discontinuation	22
		4.3.2	Patient Withdrawal	22
		4.3.3	Study Discontinuation	23
		4.3.4	Replacement Policy	23
5	STU	DY TRI	EATMENTS	24
	5.1	Study '	Treatments Administered	24
	5.2	Identit	y of Study Treatments	24
		5.2.1	RPL554 and Placebo	24
		5.2.2	Tiotropium/olodaterol Respimat®	24
	5.3	Prepara	ation and Labelling	25
		5.3.1	Nebulized RPL554 and Placebo	25
		5.3.2	Tiotropium/olodaterol	25

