1.2 Summary of Risks and Benefits

Data from non-clinical studies suggested a potential for hypotension and tachycardia. However, in the clinical studies to date RPL554 has been well tolerated in moderate to severe COPD patients, healthy subjects, asthmatics and allergic rhinitics. The most common adverse events that have been reported at least twice in subjects who have received single or multiple doses of the nebulized suspension of RPL554 were generally mild and in descending order of frequency are headache, cough, dizziness, and palpitations. Adverse events for single and multiple dose studies are summarized in Investigator's Brochure Section 6.3.

The suspension formulation of RPL554 is pH balanced, and has favorable non-clinical toxicology and pharmacokinetic data.

There has been no evidence of significant adverse events related to the cardiovascular or gastrointestinal systems, except associated with an increase in heart rate at high doses (12 mg to 24 mg). These small increases in heart rate may relate to the PDE3 inhibitory activity of the compound. In single dose studies there appears to be an increase in the rate of headache, which is most pronounced at doses over 6 mg. There was no other apparent dose related adverse events, with the exception of palpitations in patients dosed at 24 mg. In particular, Holter findings have indicated no arrhythmogenic potential in the completed studies. Results from multiple dose data in patients with COPD suggests a transient increase in dizziness, the majority of which occurred during spirometry or dosing; otherwise, the rate of adverse events was similar in RPL554 and placebo treated patients. There was an apparent increase in mild adverse events in healthy subjects treated with high doses of RPL554, which may be associated with the higher serum levels in healthy subjects than in those with obstructive lung disease.

As RPL554 is planned in this study to be administered for only 6 days (12 doses) over two treatment periods (placebo is administered in the third treatment period), any benefit to the patients will be restricted to the immediate short-term.

Verona Pharma plc CONFIDENTIAL Page 16 of 66

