9.3.2 Secondary Endpoints

- Change from baseline in trough FEV₁ on Day 4 (mean of -1 and 0 time prior to dosing)
- Determination of AUC_{0-4h} FEV₁ after morning dosing on Day 3
- Peak FEV₁ (measured in first 4 hours after dosing) and AUC_{0-12h} FEV₁. These will be measured after dosing on Day 1
- Change from baseline in AUC_{0-12h} FEV₁ measured on Day 3
- Change from pre-evening dose FEV₁ on Day 3 (peak over 4 hours)
- Determination of onset of action (>10% increase in FEV₁, from pre-first dose, censored at 120 minutes) on Day 1
- RV, FRC and sG_{aw} at 1.25 hours on Day 1 and 1.25, 8.25 and 12.25 hours after dosing on Day 3
- RPL554 steady state pharmacokinetics (AUC, C_{max} , time to maximum concentration [t_{max}])

Verona Pharma plc CONFIDENTIAL Page 49 of 66

- Safety and tolerability:
 - Continuous monitoring of adverse events
 - Laboratory safety tests [hematology, biochemistry and urinalysis]
 - 12-lead ECG (including QTcF and heart rate), supine vital signs [blood pressure and pulse rate]
 - Peak (measured in first 4 hours after dosing) and AUC_{0-4h} pulse rate for each treatment period.
 - Holter monitor results

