3.3. CHANGES TO ANALYSIS FROM PROTOCOL

Not applicable.

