16.3. ECG EVALUATIONS

Overall results from the central ECG (Electrocardiogram) Reading Center will be included in the reporting of this study. The overall assessment of ECG parameters will be reported for this study:

- Normal
- Abnormal not Clinically Significant (ANCS)
- Abnormal Clinically Significant (ACS)

The following summaries will be provided for ECG data:

Actual assessments at baseline (pre-dose at each treatment period) and each post-dose time points, including
end of study visit and overall (where overall is regardless of treatment period, day and timepoint to assess
treatment group as a whole).

Document: Z:\RPL554\UYA25849\Biostatistics\Documentation\SAP\Verona RPL554-CO-204 SAP v1.0

Author: [name] Version Number: 1.0

Version Date: [18OCT2018]

Template No.: CS_TP_BS016 Revision 5 Reference: CS_WI_BS005

Effective Date: 01Apr2018

Page 39 of 50

- Shift of overall assessment baseline to post-dose time points according to markedly abnormal criteria
- Incidence of markedly abnormal criteria
- Listing of patients meeting markedly abnormal criteria

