16.4. VITAL SIGNS

The following Vital Signs measurements will be reported for this study:

- Supine Systolic Blood Pressure (mmHg)
- Supine Diastolic Blood Pressure (mmHg)
- Supine Pulse Rate (bpm)

The following summaries will be provided for vital signs data:

 Actual assessments at screening, baseline (pre-dose at each treatment period) and each post-dose time points, including end of study visit and overall (where overall is regardless of treatment period, day and timepoint to assess treatment group as a whole).

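### The protocol synopsis plans ANCOVA comparisons of heart rate and blood pressure, but SAP 16 specifies none and SAP 3.3 declares no change, so no treatment difference with a confidence interval is planned for them

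*SAP*

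**What the plan says.** The Statistical Methods entry of the protocol synopsis states: "Treatments will be compared using analysis of covariance adjusting for treatment, period, patient and baseline". It then assigns multiplicative models to FEV1 and plethysmography, and "additive models for blood pressure, pulse rate and ECG heart rate". Protocol 9.3.2 includes 12-lead ECG heart rate, supine blood pressure and pulse rate among the safety endpoints, and adds two derived ones: peak over the first 4 hours and AUC0-4h "pulse rate for each treatment period".

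The body of the protocol is less definite. Section 9.4.5 applies ANCOVA to FEV1 and plethysmography only, and section 9.4.7 describes safety summaries by treatment group and time point, with change from baseline for continuous variables, but no model.

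SAP 16 opens its safety section with the rule "There will be no statistical comparisons between the treatment groups for safety data, unless otherwise specified with the relevant section". For vital signs, 16.4 lists "Actual assessments at screening, baseline (pre-dose at each treatment period) and each post-dose time points". For ECG, 16.3 says "The overall assessment of ECG parameters will be reported for this study", meaning normal, abnormal not clinically significant or abnormal clinically significant. Under changes from the protocol, SAP 3.3 reads "Not applicable".

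**The concern.** A model by which treatments are to be compared is an inferential plan. The synopsis has one for these three variables and the SAP does not, yet the SAP records no departure. Protocol 9.1 asks that departures from the planned analysis be detailed and justified in the study report; one that is not recognised as a departure is easily missed there.

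Tolerability and safety are a secondary objective, and protocol 1.2 says of the drug class effect: "Data from non-clinical studies suggested a potential for hypotension and tachycardia". The drug is given here on top of a long acting beta2-agonist. The crossover is justified in protocol 3.2 by its ability to compare treatments within patients. Without an interval, a reader of the results cannot tell how large a heart rate or blood pressure effect at 1.5 or 6 mg remains compatible with the data.

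**Working it through.** **Step 1. Set the texts side by side.**

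| Variable | Protocol | SAP 16 |
|---|---|---|
| Blood pressure | Synopsis: additive ANCOVA. 9.3.2: safety endpoint. 9.4.7: summaries | 16.4: actual values; no model, difference or interval |
| Pulse rate by time point | As above | 16.4: as above |
| Peak and AUC0-4h pulse rate | 9.3.2: safety endpoints | Not mentioned |
| ECG heart rate (numeric) | Synopsis: additive ANCOVA. 9.3.2: safety endpoint | 16.3: overall category only |

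The SAP rule has an exception for sections that specify a comparison. Reading 16.1 to 16.6 in turn, none uses it, so the exclusion is complete in effect.

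**Step 2. What the by-treatment summaries can and cannot give.** SAP 3.1 randomizes equally to six sequences, which together place each treatment equally often in each period. With complete data and equal sequence sizes, the difference between two treatment means equals the mean within-patient difference, and period effects cancel. Since 70/6 = 11.7 is not a whole number, and some patients will miss periods, this is approximate. So a rough point difference for blood pressure and pulse rate can be read from the tables. Its standard error cannot. For two treatments with SDs s1 and s2,

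variance of a within-patient difference = s1² + s2² − 2·ρ·s1·s2,

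and the within-patient correlation ρ is not among the planned outputs.

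**Step 3. Size of the missing interval.** The documents state no SD, margin or precision for any safety comparison, so there is no figure of the plan to reproduce. For illustration:

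- Patients: 70 (protocol 9.5), assumed complete in all three periods.
- Residual degrees of freedom: 210 observations − 70 patients − 2 treatment − 2 period − 1 baseline = 135.
- 95% half-width = t(0.975; 135) × residual SD × √(2/70), ignoring any small loss from baseline imbalance.
- Residual SD: assumed, 4 to 10 bpm or mmHg.

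| Assumed residual SD | 95% half-width |
|---|---|
| 4 | 1.34 |
| 5 | 1.67 |
| 6 | 2.01 |
| 8 | 2.67 |
| 10 | 3.34 |

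**Step 4. How many comparisons the synopsis sentence could imply.** It names no time point. Protocol 7.4.4 schedules 7 + 6 + 7 = 20 post-dose vital sign times per period, and 7.4.6 schedules 5 post-dose ECGs. Systolic pressure, diastolic pressure and pulse at 20 times, plus ECG heart rate at 5, make 65 outcomes, or 130 dose-versus-placebo contrasts. A usable plan has to name a shorter set.

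**The case against.** The strongest reply is that the commitment stands in the synopsis alone. Protocol 9.4.7, the safety analysis section, is descriptive, and on inference the SAP follows it. That stands, and it means the protocol is inconsistent with itself. A reader might infer that the SAP discarded a settled plan; the documents do not support that. But 9.4.7 does not forbid a model, so summaries and the synopsis ANCOVA can coexist, and the SAP is the place to say which applies.

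Second, the SAP is based on protocol version 2.0 of 10 July 2018, whereas the supplied protocol calls itself the first version. The synopsis sentence may have changed. This stands as a limit on the criticism of SAP 3.3 and can only be settled by checking version 2.0.

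Third, a reader might infer that the trial will give no estimate at all, or that SAP 16 forbids every comparison. Neither is right: approximate point differences for blood pressure and pulse rate are available (step 2), and the rule has an exception clause. What is missing is the adjusted within-patient difference and its interval.

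Fourth, the cardiovascular signal should not be overstated. The hypotension and tachycardia potential is non-clinical. Protocol 1.2 goes on to report good clinical tolerability, and places small heart rate increases at 12 to 24 mg, above the doses used here. This lowers the urgency; it does not remove the value of an interval at the doses studied.

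Finally, a reader might want a factor by which unpaired reading widens the interval. Both widths come from the same formula, so any such factor is only the ratio of two assumed SDs. The documents supply neither.

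**Conclusion.** The point holds as a mismatch between documents with a practical consequence. On the supplied texts, following the SAP yields by-treatment summaries of blood pressure and pulse rate, no within-patient treatment difference or confidence interval for either, no peak or AUC0-4h pulse rate result, and no numeric 12-lead ECG heart rate result. The gain in precision cannot be quantified from the documents. The interval that the design could supply would have a half-width of about 1.3 to 3.3 bpm or mmHg, resting wholly on an assumed residual SD of 4 to 10 and 70 complete patients. The primary efficacy conclusion is unaffected; the effect is on what the trial can say about its safety objective. The change should be made, subject to what protocol version 2.0 says.

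**What to change.** In SAP 16.3 and 16.4, use the exception in the section 16 rule and name the responses. For example:

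> 16.4: As an exception to the general rule of section 16, peak and AUC0-4h pulse rate and average systolic and diastolic pressure over 0-4 h, all on Day 3, will be analysed by an additive ANCOVA with treatment, period and patient as factors and the pre-dose Day 1 value of the period as covariate. Differences from placebo for RPL554 6 mg and 1.5 mg will be given with 95% confidence intervals, for estimation and without multiplicity adjustment.
>
> 16.3: ECG heart rate will be summarised numerically, and its 2-hour value on Day 3 analysed in the same way. All other safety data remain descriptive.

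Protocol 9.3.2 names no day for the pulse rate endpoints. Day 3 is suggested because it matches the primary endpoint; the sponsor may choose other days or measures, provided they are fixed before unblinding. As drafted there are 5 responses × 2 doses = 10 intervals.

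Also reconcile the synopsis with protocol 9.4.7, checking version 2.0. If the sponsor prefers to keep safety descriptive, SAP 3.3 should declare and justify that, including the omission of the pulse rate endpoints of 9.3.2.

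Cost: SAP wording and a few tables from data already collected. The FEV1 code in SAP 15.1.3 needs adapting rather than copying, because it works on the log scale and treats patient as random, whereas the protocol's FEV1 ANCOVA (9.4.5) has patient as a fixed factor. The downside is several unadjusted intervals, which must be labelled as such.

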16.1. ADVERSE EVENTS

Adverse Events (AEs) will be coded by MedDRA dictionary using the version specified in the data management plan.

Treatment emergent adverse events (TEAEs) are defined as AEs that started or worsened in severity on or after the first dose of study medication, based on the investigator assessment of severity. TEAEs will be assigned to treatment groups based on actual treatment received. TEAEs, like medications, may be assigned to multiple treatment groups due to the cross-over design of the study. This will depend on the occurrence date and duration of each TEAE.

See Appendix 2 for handling of partial dates for AEs. In the case where it is not possible to define an AE as treatment emergent or not, the AE will be classified by the worst case; i.e. treatment emergent.

Document: Z:\RPL554\UYA25849\Biostatistics\Documentation\SAP\Verona RPL554-CO-204 SAP v1.0

Author: [name] Version Number: 1.0

Version Date: [18OCT2018]

Template No.: CS_TP_BS016 Revision 5 Reference: CS_WI_BS005

Effective Date: 01Apr2018

Page 36 of 50

An overall summary of number of patients within each of the categories described in the sub-section below, will be provided as specified in the templates.

Listings will include TEAEs and Non-TEAEs.

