3 INVESTIGATIONAL PLAN

3.1 Overall Study Design and Plan Description

This is a Phase II, randomized, double blind, placebo controlled, complete block three-way crossover study to investigate treatment with nebulized RPL554 and tiotropium/olodaterol Respimat[®] in patients with moderate to severe COPD. It is planned to randomize approximately 70 patients at up to four study centers. The study comprises the following, as shown in Figure 1: Screening, three treatment periods each lasting 3 days and an end of study visit. The procedures performed at each visit are summarized in Section 6 and the study assessments are described in Section 7.

Figure 1 Study Flow Chart

Patients will be screened for eligibility, including a reversibility test with salbutamol (in UK) /albuterol (in US) and ipratropium between 7 and 14 days before the first dose of study treatment.

Eligible patients will then attend the clinic for three separate treatment periods (Treatment Periods 1 to 3), with each lasting 3 days and separated by a 7 to 14-day washout period (taken from last dose of study medication). Patients will be randomized pre-dose on Day 1 of Treatment Period 1. During each treatment period, patients will be present at the study center from the morning of Day 1 until the morning of Day 4.

In each treatment period, patients will receive an open label dose of tiotropium/olodaterol from a Respimat® device followed immediately (starting within 2 minutes) by a double-blind dose of either RPL554 or placebo (depending on treatment sequence) from a nebulizer in the morning on Day 1, Day 2 and Day 3. The dose of RPL554 or placebo will be repeated in the evening on Day 1, Day 2 and Day 3.

The assessments performed in each treatment period will be the same. Lung function (FEV₁ and forced vital capacity [FVC]) will be measured by spirometry pre-dose and up to 12 hours post-dose on Days 1 and 2 and up to 24 hours post-morning dose on Day 3 (i.e. Day 4). Whole body plethysmography will be performed pre-dose and 1.25 hours post-dose on Day 1, and pre-dose and 1.25, 8.25 and 12.25 hours post-dose on Day 3. Vital signs will be measured pre-dose and up to 12 hours post-dose on Day 1, up to 12 hours post-dose on Day 2 and up to 24 hours post-dose on Day 3 (i.e. Day 4). Electrocardiograms (ECG) assessments will be performed pre-dose and up to 4 hours post-dose on Day 1, at 2 hours post-dose on Day 2 and

Verona Pharma plc CONFIDENTIAL Page 18 of 66

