3. STUDY DESIGN

3.1. GENERAL DESCRIPTION

This is a Phase II, randomized, double blind, placebo controlled, complete block three-way crossover study to

Document: Z:\RPL554\UYA25849\Biostatistics\Documentation\SAP\Verona RPL554-CO-204 SAP v1.0

Author: [name] Version Number: 1.0

Version Date: [18OCT2018]

Template No.: CS_TP_BS016 Revision 5 Reference: CS_WI_BS005

Effective Date: 01Apr2018

Page 11 of 50

investigate treatment with nebulized RPL554 and tiotropium/olodaterol Respirat® in patients with moderate to severe chronic obstructive pulmonary disease (COPD).

A total of approximately 70 male or female COPD patients (as defined by the American Thoracic Society [ATS]/European Respiratory Society [ERS] guidelines with symptoms compatible with COPD for at least 1 year prior to Screening) aged 40 to 80 years (inclusive) will be randomized across up to 4 sites, in the Unites States (US) and the United Kingdom (UK). All patients will receive 3 combinations of study treatment (1.5 mg RPL554, 6 mg RPL554 and placebo) in a randomized, crossover design; therefore, each patient will act as his or her own control in the study. There are 6 possible treatment sequences a patient can be randomized to: a) RPL544 1.5 mg / RPL544 6.0 mg/Placebo, b) RPL544 1.5 mg / Placebo / RPL544 6.0 mg, c) RPL544 6.0 mg / RPL544 1.5 mg / Placebo, d) RPL544 6.0 mg / RPL544 1.5 mg, e) Placebo / RPL544 1.5 mg / RPL544 6.0 mg and f) Placebo / RPL544 6.0 mg / RPL544 1.5 mg, with the ratio of patients to treatment groups / treatment sequences being 1:1:1:1:1:1.

Patients will be screened for eligibility, including a reversibility test with salbutamol (in UK) or albuterol (in US) and ipratropium between 7 and 14 days before the first dose of study treatment. Eligible patients will then attend 3 separate treatment periods (Treatment periods 1 to 3), with each lasting 3 days and separated by a 7 to 14-day washout period. Figure 1 below summarizes these details.

Document: Z:\RPL554\UYA25849\Biostatistics\Documentation\SAP\Verona RPL554-CO-204 SAP v1.0

Author: [name] Version Number: 1.0

[figure not shown]
Version Date: [18OCT2018]

Template No.: CS_TP_BS016 Revision 5 Reference: CS_WI_BS005

Effective Date: 01Apr2018

Figure 1 Study Flow Chart

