6.3. REPEAT/RESCHEDULE, UNSCHEDULED VISITS AND EARLY TERMINATION DATA

In general, for by-visit summaries, data recorded at the nominal visit will be presented. If a visit is repeated/rescheduled due to variability in FEV₁ or other reason, the repeated/rescheduled visit, will be listed and summarized as the valid visit (same visit number assigned), at the discretion of the Investigator. Unscheduled measurements will not be included in by-visit summaries, but will contribute to the endpoint value, at the discretion of the Investigator. For example, if an unscheduled visit occurred at 10 hours post-dose on Day 3, then this value will be considered in the calculation of the average FEV₁ over 12 hours (AUC_{0-12h} FEV₁) on Day 3. Any unscheduled or unplanned readings will be presented within the patient listings.

Early termination data will be mapped according to the visit number the termination occurred for by-visit summaries. If early termination occurs pre-first dose (after baseline), then it is summarized at the actual visit. If

Document: Z:\RPL554\UYA25849\Biostatistics\Documentation\SAP\Verona RPL554-CO-204 SAP v1.0

Author: [name] Version Number: 1.0

Version Date: [18OCT2018]

Template No.: CS_TP_BS016 Revision 5 Reference: CS_WI_BS005

Effective Date: 01Apr2018

Page 17 of 50

termination is after first dose in period or during the following wash-out period, data collected remains at the visit performed. However, if the patient returns for end of study, then this data will be mapped to end of study visit.

If AE data occurs in the 7 to 14-day gap between treatment periods, these will be mapped to the earlier of the two treatment periods. Similarly, the AE will be mapped to the last treatment group received. If AE data occurs in the post-treatment period, these will be mapped to the last treatment period and last treatment group received.

Listings will include scheduled, unscheduled, repeat/reschedule and early discontinuation data.

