APPENDIX 2. Partial Date Conventions

Imputed dates will NOT be presented in the listings.

Document: Z:\RPL554\UYA25849\Biostatistics\Documentation\SAP\Verona RPL554-CO-204 SAP v1.0

Author: [name] Version Number: 1.0

Version Date: [18OCT2018]

Template No.: CS_TP_BS016 Revision 5 Reference: CS_WI_BS005

Effective Date: 01Apr2018

ALGORITHM FOR TREATMENT EMERGENCE OF ADVERSE EVENTS

START DATE	STOP DATE	ACTION
Known	Known	If start date < study med start date, then not TEAE
		If start date >= study med start date, then TEAE
	Partial	If start date < study med start date, then not TEAE
		If start date >= study med start date, then TEAE
	Missing	If start date < study med start date, then not TEAE
		If start date >= study med start date, then TEAE
Partial, but known	Known	Not TEAE
components show that it		
cannot be on or after study		
med start date		
	Partial	Not TEAE
	Missing	Not TEAE
Partial, could be on or after	Known	If stop date < study med start date, then not TEAE
study med start date		If stop date >= study med start date, then TEAE
	Partial	Impute stop date as latest possible date (i.e. last day of month
		if day unknown or 31st December if day and month are
		unknown), then:
		If stop date < study med start date, then not TEAE
		If stop date >= study med start date, then TEAE
	Missing	Assumed TEAE
Missing	Known	If stop date < study med start date, then not TEAE

Document: Z:\RPL554\UYA25849\Biostatistics\Documentation\SAP\Verona RPL554-CO-204 SAP v1.0

Author: [name] Version Number: 1.0

Version Date: [18OCT2018]

Template No.: CS_TP_BS016 Revision 5 Reference: CS_WI_BS005

Effective Date: 01Apr2018

Page 48 of 50

START DATE	STOP DATE	ACTION
		If stop date >= study med start date, then TEAE
	Partial	Impute stop date as latest possible date (i.e. last day of month
		if day unknown or 31st December if day and month are
		unknown), then:
		If stop date < study med start date, then not TEAE
		If stop date >= study med start date, then TEAE
	Missing	Assumed TEAE

ALGORITHM FOR PRIOR / CONCOMITANT MEDICATIONS

START DATE	STOP DATE	ACTION	
Known	Known	If stop date < study med start date, assign as prior	
		If stop date >= study med start date and start date <= end of treatment,	
		assign as concomitant	
		If stop date >= study med start date and start date > end of treatment, assign	
		as post study	
	Partial	Impute stop date as latest possible date (i.e. last day of month if day	

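### The SAP's overlap rule lets a persisting adverse event be counted again under the next treatment, placebo included, with no new onset or worsening

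*SAP*

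**What the plan says.** Three parts of the SAP bear on which treatment an adverse event is counted under.

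- **Section 16.1** defines treatment-emergent events as "AEs that started or worsened in severity on or after the first dose of study medication". It then says "TEAEs, like medications, may be assigned to multiple treatment groups due to the cross-over design of the study" and adds: "This will depend on the occurrence date and duration of each TEAE".
- **Section 6.3** deals with events outside the dosing days: "If AE data occurs in the 7 to 14-day gap between treatment periods, these will be mapped to the earlier of the two treatment periods". It continues: "Similarly, the AE will be mapped to the last treatment group received". Events after the end of treatment go to the last period and the last treatment.
- **Appendix 2** decides emergence from a single study-level date: "If start date >= study med start date, then TEAE". It does not assign a treatment.

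Sections 16.1 and 6.3 do not refer to each other. The severity and relationship summaries in 16.1.1 add no rule by period. Protocol 9.4.7 asks for events by treatment group and does not mention an event that spans two periods.

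**The concern.** Duration can affect the assignment only if an event is counted under each treatment it overlaps. The comparison with medications supports that reading, since SAP section 12 lets a medication count once in every period in which it occurs. That suits a drug actually taken in both periods. It does not suit an event that emerged once.

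Because emergence is tested only against the first study dose, nothing requires the event to start or worsen under the second treatment. An unchanged event from an RPL554 period, including one judged related or serious, may then also appear in the placebo column.

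Safety and tolerability is a secondary objective. SAP section 16 plans no between-treatment safety tests by default, so readers will judge safety from these counts. A rule that pulls the columns together makes a real excess on RPL554 harder to see.

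**Working it through.** The plan states no figure on this point, so there is none to reproduce. The check compares the rules and then estimates the size under stated assumptions.

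**1. The rules applied to three events**

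| Event | SAP 6.3 | SAP 16.1 |
|---|---|---|
| Starts and ends within one dosing period | Not addressed | One treatment |
| Starts on a dosing day, still present in the next period | Silent, if occurring means onset | Both treatments allowed |
| Starts in the washout, still present in the next period | Earlier treatment only | Both treatments allowed |

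Only the third row is a clear conflict. In the second row the difficulty is the open rule in 16.1 itself.

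**2. How long an event must last**

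The washout runs 7 to 14 days from the last dose on Day 3 (Protocol 3.1). An event starting at about that dose must last at least about 7 days to reach the next period. One starting on Day 1 before the longest washout needs about 14 + 2 = 16 days. An event starting within the washout needs only the remainder of it.

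**3. First-order effect on the contrast**

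The six sequences are equally allocated: "with the ratio of patients to treatment groups / treatment sequences being 1:1:1:1:1:1". Each treatment comes first in one third of sequences and directly follows each other treatment in one third. Let p be the onset rate on a treatment and c the fraction of events lasting into the next period. Ignoring patients who already have an event:

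- observed 6 mg = p(6) + (c/3)[p(1.5) + p(P)]
- observed placebo = p(P) + (c/3)[p(1.5) + p(6)]
- difference = [p(6) - p(P)] × (1 - c/3)

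Both rates rise and the difference shrinks. If the true rates are equal, the expected difference stays zero.

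**4. Patient-level calculation**

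Assumed onset rates are 15% (6 mg), 10% (1.5 mg) and 6% (placebo). An event reaches the next period with probability c and the one after that with probability c². Incidence on treatment t is:

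- period 1: p(t)
- period 2: 1 - [1 - p(t)][1 - c·p(previous)]
- period 3: 1 - [1 - p(t)][1 - c·p(previous)][1 - c²·p(first)]

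Placebo at c = 30%:

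- placebo first (two sequences): 6.00% each
- second, after 6 mg: 1 - 0.94 × 0.955 = 10.23%
- second, after 1.5 mg: 1 - 0.94 × 0.97 = 8.82%
- third, after 6 mg then 1.5 mg: 1 - 0.94 × 0.97 × 0.9865 = 10.05%
- third, after 1.5 mg then 6 mg: 1 - 0.94 × 0.955 × 0.991 = 11.04%
- mean: 52.14 / 6 = 8.69%

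Repeating this for 6 mg and other values of c:

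| c | 6 mg | Placebo | Risk difference (points) | Risk ratio |
|---|---|---|---|---|
| 0 | 15.0% | 6.0% | 9.0 | 2.50 |
| 5% | 15.2% | 6.4% | 8.8 | 2.38 |
| 10% | 15.5% | 6.8% | 8.7 | 2.27 |
| 30% | 16.6% | 8.7% | 7.9 | 1.91 |
| 50% | 17.8% | 10.8% | 7.0 | 1.64 |

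Among 70 patients, the added placebo patients number about 0.3 at c = 5%, 0.6 at 10% and 1.9 at 30% (70 times the rise in the placebo rate). The assumed 1.5 mg rate matters: at c = 30%, varying it from 6% to 15% moves observed placebo from 8.3% to 9.2%.

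**The case against.** The strongest reply is that the effect is likely to be minor. Protocol 1.2 describes adverse events that are mostly mild (headache, cough, dizziness, palpitations) and calls the dizziness seen with multiple dosing transient. Protocol 1.1 gives a half-life of about 10 to 12 hours. Few events that start during dosing should outlast the washout. The listings include every event and start and stop times are recorded, so a spanning event can be traced. The table templates, which may say more, are not among the documents. SAP 16.1 also permits multiple assignment rather than requiring it, and recounting is reasonable when an event worsens on a later treatment. All of this stands and limits the size. It does not close the gap, because no text confines the recount to worsening. Protocol 7.4.1.2.2 also provides a category for persistent events.

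Two stronger readings are tempting, and the documents support neither:

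- A reader might infer that events are moved from RPL554 to placebo and so hidden. Under 16.1 the treatment of onset keeps its count, and placebo-onset events are likewise added to RPL554. The 6 mg rate is overstated, and only the contrast is diluted.
- A reader might infer that 6.3 is a general single-assignment rule that 16.1 contradicts throughout. It covers only events in the gap and after treatment.

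**Conclusion.** The point holds as a defect in the counting rule, with an effect that is probably small. SAP 16.1 and Appendix 2 together allow an unchanged event to count as treatment-emergent under a treatment on which it neither began nor worsened. On average this attenuates the descriptive RPL554-placebo contrast. The conflict with 6.3 is confined to an event that starts in the washout and continues into the next period, where two programmers could produce different tables.

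Every figure for size rests on assumed onset rates and an assumed c. At c of 5% to 10% the risk difference falls from 9.0 to 8.8 or 8.7 points. The values at 30% and 50% show how the rule behaves if persistence is common, and a reader should not take them as expected. Nothing in the documents supports persistence that high. The change is still worth making before unblinding, because safety is read from these counts and the rule is easily settled.

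**What to change.** In SAP 16.1, count each treatment-emergent event only under the treatment period in which it started. Washout and post-treatment onsets go to the preceding treatment, as in 6.3. Count the event again under a later treatment only if a worsening in severity is recorded on or after that period's first dose, for example as a new adverse event record with its own start date. Cross-refer 16.1 and 6.3, change Appendix 2 so that emergence is judged by period, and flag period-spanning events in the listing.

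The cost is a short SAP amendment and minor programming. One data need goes with it: worsening must carry a date. Protocol 7.4.1.2 records start and stop times and a severity grade, and describes no date of worsening. Its severity grades turn on how an event resolved or was tolerated with treatment, so the eCRF instructions should say how a worsening is entered.
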